4.2 Data quality checks

We have several questions in the survey that capture respondent attention. We will check that low quality survey responses are not affected by the treatments. If they are not, we will exclude low quality survey responses. We also plan to exclude those that take very little time on the survey overall and/or on the videos.

5. Empirical Analysis

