2.3 Experimental Protocols and Treatments

Our experiment has the following structure:

1. Recruitment and Baseline survey
 - (a) Recruit target sample via Lucid
 - (b) For Hispanic respondents, elicit a preference for English or Spanish. Those with a preference for Spanish will be given Spanish language survey questions and will see treatment videos recorded in Spanish as well.⁴
 - (c) Collect demographic information and healthcare experience. Several demographics variables are being collected directly by Lucid.
2. Randomize Subjects to treatment
 - Treatment scripts are tailored to each racial/ethnic group
 - Within racial/ethnic group, treatment is stratified on age, gender and geographic region.
 - Randomization is at the individual level according to Figure 1.
 - There will also be a control group who will receive COVID-19 information at the very end of the survey.
3. Video delivery for all individuals not in the pure control group.
 - (a) After each of the three videos, respondents evaluate the video's usefulness, and trustworthiness, along with the respondents intention to follow the advice in the video and share information from the video.
 - (b) Prior to the third video (masks), individuals will answer questions about second order beliefs about mask wearers.
4. Endline survey
5. Videos shown to the pure control group.
6. Debrief script
7. Follow-up survey
 - (a) We are tentatively planning to follow up with participants several days post-treatment
 - (b) The chief purpose would be to measure health-seeking and health-preserving behaviors.⁵
8. Once we learn which messaging strategy is most effective, we will scale up that treatment more broadly (distributing it through social media etc.)

⁴The one exception is the CDC video with [name]. This is always shown in English.

⁵We do not commit on analyzing this data or even fully implementing a follow up because it is quite difficult to successfully follow up with online survey participants, so it will depend on our success in finding people in our pilot.

3. General Hypotheses to be Tested

This section lists the general hypotheses we want to test. For those, we are planning to run broadly pooled treatments (and specific interactions specified below).

Main hypotheses:

1. What is the overall effect of any combination of videos, compared to the control group?
2. Does racial concordance between the doctor messenger and recipient give the message higher impact across the board?

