In addition to testing these hypotheses, we will also explore what is the most effective combination of messages and messengers overall (after “smart statistical pooling” of variants that prove similar), and what is its effect, accounting for any small sample bias induced by picking a winner.

4. Data Collection and Outcomes

We will run our experiment beginning on May 13, 2020. The data will be collected from respondent surveys. There is a short baseline module before the treatment group views the videos. Before the mask video (video 3), we elicit beliefs about perceptions of mask wearers. Then following video 3, there is an endline outcome module that all participants complete. (The control group only sees the videos after the endline has been completed.) We may decide at a later date to do a follow up survey with a subsample of the original participants. (Clearly, for this exercise, there will no longer be a valid control group. All comparisons will be done across treatments.) All of the survey responses will be downloaded is a .csv file for cleaning and analysis in STATA.

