4.1 Baseline Survey Variables

The baseline survey includes demographic characteristics, information about health status, and access to healthcare:

- Education
- Household Size
- Employment Status
- Essential Worker Status
- Insurance Status
- Pre-Existing Health Conditions
- Healthcare Usage Patterns
- Health Information Sources
- Food Security

See Section 5, below for a summary of our key Endline survey variables.

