5.1 Balance Checks

We will conduct a series of balance tests across treatment arms to ensure that there are no chance differences between subjects in the various arms. We will regress characteristics measured pre-treatment on indicators for the arms and test their individual and joint significance. Balance tests will be conducted using all of the variables measured in the baseline survey.

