5.2 Key Outcomes

We intend to measure the treatment effects on the following families of outcomes. Outcomes marked (T) pertain to trust in the medical system or in health information. Outcomes marked (SD-H) pertain to the social distancing and hygiene content from the CDC video. Outcomes marked (M) pertain to mask-wearing.

1. Attention and Assessments (T):
 - (a) Ratings and trust, willingness to share videos as described above,
 - (b) Time spent watching the videos
2. Knowledge of information presented in the video (retention)
 - (a) Basic information about symptoms
 - (b) Information covered in the CDC video (SD-H)
 - (c) Information covered in the mask video (M)
3. Measures related to trust in the health-care system and health-seeking behavior (T).
4. Views on Mask-wearing (M)
5. Interest in more information about masks and allocations to organizations supporting mask-wearing (M)
6. Interest in more information pertaining to social distancing and hygiene (SD-H)

We will construct indices for each family, where applicable. We will also adjust our inferences for multiple outcome testing.

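### Excluding people for short video viewing selects on a post-randomisation outcome that controls lack before the endline, so the treatment-versus-control test can be biased

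*Combined protocol and SAP*

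**What the plan says.** Section 4.2 (Data quality checks) has two exclusions. The first concerns low-quality responses and is conditional: "We will check that low quality survey responses are not affected by the treatments", followed by "If they are not, we will exclude low quality survey responses". The second concerns time: "We also plan to exclude those that take very little time on the survey overall and/or on the videos". That sentence gives no cut-off, repeats no condition and does not mention the control group.

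Section 5.2 (Key Outcomes) lists "Time spent watching the videos" as item (b) of outcome family 1.

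Section 2.3 places randomisation at step 2 and the videos at step 3, for everyone outside the pure control group. Of controls it says: "There will also be a control group who will receive COVID-19 information at the very end of the survey". Section 4 (Data Collection and Outcomes) confirms the order: "The control group only sees the videos after the endline has been completed".

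Main test 1 in section 5.3 compares treatment with control, separately for Black and Hispanic respondents.

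**The concern.** Randomisation makes the groups comparable at the moment of assignment. A screen applied afterwards keeps them comparable only if it removes the same kinds of people from each group. Short viewing in the video arms marks people with low attention. Controls with equally low attention have no viewing time before the endline, so this part of the rule cannot identify them in the same way. If attention is related to knowledge, trust or interest in masks, the retained treated group differs from the retained controls even when the videos do nothing.

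Two further effects follow. Outcome 1(b) is cut off at its lower end in every video arm, because the rule filters on the quantity being analysed. And main hypothesis 5 asks whether the CDC video makes people stop attending to what follows; the rule can remove some of the people who show exactly that effect.

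The open cut-off adds to the problem, because the share removed is left to be chosen after the data are in.

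**Working it through.** The plan gives no figure for this rule: no cut-off, expected exclusion rate or control share. There is nothing to reproduce, and what follows is an illustration.

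**Inputs from the documents.** N = 10,000 Black and 5,000 Hispanic respondents (section 2.2); 16 treatment cells (section 5.3).

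**Assumed inputs.**
- Outcome SD 1, no true effect, two-sided 5% test.
- Control share from 1/17 (a control group the size of one cell) to 20%.
- Correlation rho between attention and outcome: 0.1 or 0.3.
- The least attentive share q of treated people is removed: 5% or 10%.
- s is the share of equivalent controls removed by any other route: 0, 0.5 or 1.

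**Formulas**, with phi(z_q) the normal density at the q-quantile:
- Outcome difference, kept minus removed: d = rho × phi(z_q) / [q(1 − q)]
- Bias = q × d × (1 − s) / (1 − s × q)
- SE = sqrt{1/[nT(1 − q)] + 1/[nC(1 − s × q)]}
- Type I error = P(Z > 1.96 − bias/SE) + P(Z < −1.96 − bias/SE)

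**Black sample, rho 0.3, q 10%.** phi(z_q) = 0.1755, so d = 0.3 × 0.1755 / 0.09 = 0.585.
- s = 0: bias = 0.1 × 0.585 = 0.0585 SD. With control share 1/17 (nC = 588, nT = 9,412), SE = 0.0426, the ratio is 1.37 and type I error is 28%. With control share 20% (nC = 2,000, nT = 8,000), SE = 0.0253, the ratio is 2.31 and type I error is 64%.
- s = 0.5: bias = 0.0585 × 0.5 / 0.95 = 0.0308 SD. SE is 0.0437 or 0.0258, and type I error is 11% or 22%.
- s = 1: bias 0, type I error 5%.

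**Black sample, rho 0.1, q 5%.** phi(z_q) = 0.1031 and d = 0.217. Bias is 0.011 SD (s = 0) or 0.006 SD (s = 0.5); type I error is 6–7% or 5–6%.

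**Hispanic sample, rho 0.3, q 10%.** The biases are the same and the SEs larger: type I error is 16–37% (s = 0) or 8–13% (s = 0.5).

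**Sign.** If other screens remove more controls than treated people (15% against 10%, rho 0.3), the bias is 0.3 × 0.1755/0.90 − 0.3 × 0.2332/0.85 = −0.024 SD.

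**Between video arms.** All have pre-endline viewing time, so exclusion rates can be compared. With 17 equal arms, the four CDC-video cells hold 2,353 Black respondents against 7,059 in the other video cells. A pooled two-proportion test of 12% against 10% short viewing has 77% power (49% in the Hispanic sample, 1,176 against 3,529). For 15% against 10%, power exceeds 99% in both.

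**The case against.** The strongest reply is that section 4.2 already contains the safeguard. Its heading is about quality checks, and the word *also* can be read as placing the time rule under the same condition. Low-quality responses would then be dropped only if treatment does not affect them, which implies keeping everyone when it does. That reading is reasonable. A reader might infer that the time exclusion is plainly unconditional, or that the plan has no fallback if quality differs by arm; the text supports neither. It does not rescue main test 1, however, because short pre-endline viewing does not exist in controls and so cannot be compared with control.

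Second, controls do see the videos at the end, and the exclusion sentence is not limited to any arm, so it could literally reach that late viewing. Overall survey time and the attention questions can also remove low-effort controls. All of this stands, and it makes s = 0 a worst case. But viewing after the endline is not equivalent to viewing before it. Overall time is itself post-randomisation, and the plan does not say whether it includes the videos.

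Third, the illustration ignores adjustment for strata (age, gender, region), which may absorb part of the bias. The balance tests and the Lasso check may also help. They work through baseline variables, and the list in section 4.1, described as "The baseline survey includes demographic characteristics, information about health status, and access to healthcare", names no attention measure. The position of the attention questions is not stated.

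Fourth, section 6.2 checks for differential attrition and may count some of these removals. It starts from people who have viewed the video, so it does not settle the handling of controls.

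**Conclusion.** The point holds for comparisons with control, chiefly main test 1, and for the truncation of outcome 1(b). It should be fixed. The textual finding is firm; the size is not. In the Black-sample illustration the bias runs from zero, if other screens remove all equivalent controls, through 0.03 SD (type I error 11–22%) to 0.06 SD (28–64%) at correlation 0.3 with 10% removed. At correlation 0.1 with 5% removed, type I error is 5–7%. All of this rests on assumed correlations, exclusion rates and control shares, and the sign can reverse.

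Two stronger conclusions are tempting. A reader might infer that main test 1 will be seriously biased; the largest figures need no low-effort control to be caught by any route, and the documents do not say that. A reader might also infer that every main contrast is compromised. Between video arms viewing time is comparable and differential exclusion can be checked, so hypothesis 5 is a secondary concern. Equal exclusion rates would still not show that the same kinds of people were removed.

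**What to change.** In section 4.2, define the primary analysis as everyone randomised with an observed endline, analysed as assigned, with no exclusion on video time or on any total time that includes the videos. Use video time only as an outcome. Report the short-time exclusion as a labelled sensitivity analysis, with the cut-off fixed in advance and the handling of controls stated. If a quality screen is wanted in the primary analysis, base it on time spent in the baseline module, which precedes the videos and exists in all arms.

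This is a change of wording and needs no new survey items. The cost is that inattentive respondents stay in and dilute effects roughly in proportion to their share: if 10% are inattentive and show no effect, the estimate is about 0.9 of the effect in the rest, a loss of about 10%. The change does not deal with drop-out before the endline, which treated people reach only after three videos; that belongs to section 6.2.

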5.1 Balance Checks

We will conduct a series of balance tests across treatment arms to ensure that there are no chance differences between subjects in the various arms. We will regress characteristics measured pre-treatment on indicators for the arms and test their individual and joint significance. Balance tests will be conducted using all of the variables measured in the baseline survey.

5.2 Key Outcomes

We intend to measure the treatment effects on the following families of outcomes. Outcomes marked (T) pertain to trust in the medical system or in health information. Outcomes marked (SD-H) pertain to the social distancing and hygiene content from the CDC video. Outcomes marked (M) pertain to mask-wearing.

1. Attention and Assessments (T):
 - (a) Ratings and trust, willingness to share videos as described above,
 - (b) Time spent watching the videos
2. Knowledge of information presented in the video (retention)
 - (a) Basic information about symptoms
 - (b) Information covered in the CDC video (SD-H)
 - (c) Information covered in the mask video (M)
3. Measures related to trust in the health-care system and health-seeking behavior (T).
4. Views on Mask-wearing (M)
5. Interest in more information about masks and allocations to organizations supporting mask-wearing (M)
6. Interest in more information pertaining to social distancing and hygiene (SD-H)

We will construct indices for each family, where applicable. We will also adjust our inferences for multiple outcome testing.

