2.1 Treatments

Each subject watches three videos. Each video features a different doctor. All partner doctors viewed in the videos by a given subject are of the same racial or ethnic background.²

1. Video 1:

- Introduction
- Discussion of symptoms
- Acknowledgement of “elephant in the room” issues, where applicable.

2. Video 2:

- Information about social distancing and hygiene

3. Video 3:

- Information about masks

We are varying four aspects of the videos across treatments:

1. Racial or ethnic concordance with partner doctors in the videos (note that we side-step the issue of language: for Spanish speakers, they can chose English or Spanish, and there are non ethnically Hispanic doctors speaking in Spanish).³
2. Video 1 content: Elephant in the room
 - No elephant in the room content
 - Elephant in the room 1: Trust or Fear
 - Elephant in the room 2: Economic Inequality

²However, some individuals may see two black doctors and [name] from the CDC, a white doctor and representative of the US government.

³However we do not have recordings in other languages.

3. Identity of the doctor delivering Video 2

- Pre-recorded video of [name] of the CDC in front of the White House
- Partner doctor

4. Video 3 content: mask debiasing

- Basic mask information, no perceptions information
- Basic mask information, perceptions information
 - For the latinx community, the video discusses perceptions that the mask-wearer is sick.
 - For the black community, the video discusses perceptions that the mask-wearer is “up to no good.”
 - In both cases the message reports responses from a prior survey of perceptions that mask wearers in photos of the same racial/ethnic group are “protecting the community.”

All of the video scripts can be found in Appendix Section A. Figure 1 shows how these different treatments are incorporated in the randomization design.

Figure 1: Treatment Design: There are 8 content-variants for each video, shown here. Cell 1c/d includes the baseline information package. For each combination of message content, the partner doctors in the video may either be of a concordant (c) or discordant (d) racial/ethnic background.

All treatments receive basic information +	Doctor-Delivered CDC Message	[name] -Delivered CDC Message	Elephant 1: Fears (L) or Trust (A)	Elephant 2: Economic Inequality
No Mask Debiasing	1c/d	2c/d	3c/d	4c/d
Mask Debiasing	5c/d	6c/d	7c/d	8c/d

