3. Does addressing the “elephant in the room” lead to greater video impact?
4. Are the doctors in our videos more effective at communicating the same message with underserved populations than [name], a representative of the CDC and the US federal government’s response? (To test this hypothesis, we will focus on the outcomes associated with the social distancing and hygiene video.)
5. Does the [name] video lead to a "shut down" and refusal to pay attention to the rest of the message: for this we can compare the attitude to masks (which are not mentioned in the [name] video, and are discussed in a video segment shown after that with [name]).
6. Does providing information on perceptions about mask wearers change an individual’s willingness to wear a mask? We proxy for willingness to wear a mask in two key ways: a) demand for information about mask-making, b) incentivized allocations of money to support masks for black or latinx communities vs. other charitable projects targeted at the same communities.
 - (a) Focus groups and baseline data suggest that on average, members of the black community worry that they will be viewed as “up to no good” when wearing a mask by a larger percent of Americans than actually hold that belief. For Latinx communities, the fear is more that mask-wearers will be perceived to be sick, generating a different kind of stigma.
 - (b) Specifically, we predict that the effects of the “social norm debiasing” treatment should vary with the respondent’s priors about how mask-wearers are viewed. Individuals learning that their beliefs were too pessimistic should increase their willingness to wear a mask, while those learning that their beliefs were too optimistic (this should be rare) might respond the opposite way.

Secondary hypotheses involving specific interactions between treatments:

1. Racial concordance might also give more credibility to other information presented in the videos such as info delivered by [name] of the CDC or information about mask perceptions.
2. Does addressing the “elephant in the room” increase impact of the videos more for discordant doctor messengers?
3. Does acknowledging the “elephant in the room” give greater credibility to other information in the video, such as the CDC video or the mask debiasing information? (Interaction effects with CDC treatment and with mask debiasing treatment.)

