5.3 Regression Analysis

We will do two types of analysis: identifying effective videos in our sample, and general tests of the hypotheses described above.

- Best treatment

We are interested in selecting the best combination of types of video for scale up. In order to identify the most effective combination of videos, we will adapt a disciplined pooling methods of Banerjee et al (2020) for selecting the most effective combination of treatments (to a settings were we have large

sample within each of 16 treatment cells), and Andrews et al (2020) to correct for small sample bias in estimating the impact the most effective method.⁶

For this specific question of whether *our* messages of a given type (concordant race, correcting priors, etc), since random assignment is done by individuals, we do not adjust standard errors. This is the correct analysis for scaling up these videos per-se.

- Hypothesis tests

In order to test the hypotheses listed above, we run the following contrasts (Hispanic and Black will be run separately for all the contrasts:

Main hypotheses tests:

1. Is there any impact of the videos (treatment vs control)
2. Concordant vs. discordant messengers: pooled across all
3. [name] with "no elephant" and the two different versions of "elephant in the room", no [name] each compared to the "no elephant, no [name]" condition
4. [name] versus everything else.
 - For social distancing and hygiene (largest effect expected here for the [name] treatment)
 - For other outcomes
5. Mask-debiasing treatment on mask outcomes, heterogenous based on respondent prior beliefs (lower or higher than 8 out of 10 people think mask wearer is helping the community).

Secondary hypotheses tests

1. [name] treatment effects will be interacted with concordant doctor
2. [name] treatment effect will be interacted with social debiasing treatment (which may be less effective after presenting [name])
3. Elephant treatment will be interacted with concordant doctor
4. Mask treatment effect will be interacted with concordant doctor
5. Mask treatment effect will be interacted with elephant treatment
6. [name] treatment effect will be interacted with elephant treatment
7. Gender of provider will be interacted with concordant doctor and/or respondent gender

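### If the family 1 index pools all three videos, its Video 1 part, rated before the CDC clip is shown, dilutes test 3, distorts test 4 and goes unused as a covariate

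*Combined protocol and SAP*

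**What the plan says.** Section 2.1 sets a fixed order of three videos and says where each content factor enters. The first is "Video 1 content: Elephant in the room". The next is "Identity of the doctor delivering Video 2", which is either a partner doctor or "Pre-recorded video of [name] of the CDC in front of the White House" (below, the CDC clip). Mask debiasing enters at Video 3. Doctor concordance applies from Video 1 on.

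Section 2.3, step 3(a), states when ratings are taken: "After each of the three videos, respondents evaluate the video's usefulness, and trustworthiness", with intention to follow the advice and to share.

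Section 5.2 defines family 1, tagged (T), as "Ratings and trust, willingness to share videos as described above" plus viewing time. Neither item is split by video. It then says: "We will construct indices for each family, where applicable". No weights or list of videos are given.

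Section 5.3 tests the CDC clip in main test 3 (against the no-elephant, no-clip condition, with no restriction on outcomes), in main test 4 (against everything else, including "For other outcomes"), and in interactions. The named controls are strata, race/ethnicity and language choice. A Lasso selection of controls is planned as a robustness check, without a candidate list. No earlier-video rating is named as a covariate or placebo outcome.

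**The concern.** A respondent's rating and viewing time for Video 1 are fixed before any CDC footage appears. In an index over three videos, part of the outcome therefore cannot respond to the factor under test.

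That part is also a pre-exposure measurement from the same respondent on what appear to be the same items, and it is likely to predict the later ratings. The plan counts it in the outcome and does not name it as a covariate. At stake is the family 1 answer on the CDC clip: a weak result on trust and attention could be read as the clip being as well received as the partner doctors, when part of the index could not have moved.

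**Working it through.** The plan states no alpha, power, effect size, SD, rating correlation or control share, so it has no figure of its own to reproduce. Its counts agree: 8 content variants x 2 = 16 cells, and 10,000 + 5,000 = 15,000 respondents.

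**Step 1: which cells.** By Figure 1, with concordant and discordant versions counted, the CDC clip is in 4 cells (2, 6), neither clip nor elephant content in 4 (1, 5), and elephant content in 8 (3, 4, 7, 8). Test 3 for the clip is 2/6 v 1/5, with identical Video 1 content. Test 4 is 4 cells v 12, and 8 of the 12 carry elephant content.

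**Step 2: dilution in test 3.** Assume equal weights, standardised ratings with common correlation rho, and clip effects 0, d2, d3 on Videos 1, 2, 3.

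- Raw effect: (d2+d3)/3 on three videos against (d2+d3)/2 on Videos 2-3, so two-thirds as large. If only Video 2 responds, the three-video effect is d2/3.
- SD of the three-video mean: sqrt((1+2rho)/3). SD of the Videos 2-3 mean: sqrt((1+rho)/2).
- Residual variance of the Videos 2-3 mean given Video 1: (1+rho)/2 - rho^2 = (1-rho)(1+2rho)/2.

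The sample that the three-video index needs, relative to Videos 2-3, is 1.5(1+2rho)/(1+rho) unadjusted and 1.5/(1-rho) adjusted for Video 1. Both involve only d2+d3, which cancels.

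| rho (assumed) | v Videos 2-3 | v Videos 2-3 adjusted for Video 1 |
|---|---|---|
| 0.2 | 1.5 x 1.4/1.2 = 1.75 | 1.5/0.8 = 1.9 |
| 0.5 | 1.5 x 2.0/1.5 = 2.0 | 1.5/0.5 = 3.0 |
| 0.7 | 1.5 x 2.4/1.7 = 2.12 | 1.5/0.3 = 5.0 |

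**Step 3: illustrative power for 2/6 v 1/5.** Assume two-sided 5%, rho 0.5, d2 = -0.10 SD, and the control group as a 17th equal cell. That gives 4 x 10,000/17 = 2,353 African American and 4 x 5,000/17 = 1,176 Hispanic respondents per side. Control shares from 0 to 20% give 2,500 to 2,000 and 1,250 to 1,000. Entries are African American / Hispanic.

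| Outcome | d3 = 0 | d3 = -0.05 | d3 = -0.10 |
|---|---|---|---|
| Three-video index | 29% / 17% | 56% / 32% | 80% / 51% |
| Videos 2-3 | 51% / 29% | 84% / 56% | 98% / 80% |
| Videos 2-3, adjusted for Video 1 | 68% / 40% | 95% / 73% | >99% / 93% |
| Video 2 alone | 93% / 68% | 93% / 68% | 93% / 68% |
| Video 2 alone, adjusted for Video 1 | 98% / 80% | 98% / 80% | 98% / 80% |

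A 3,000-run simulation of the African American d3 = -0.05 case gave 55%, 85% and 95% for the first three rows.

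**Step 4: test 4.** Let e be the elephant effect on Video 1 ratings, with equal cells. The Video 1 difference, clip minus rest, is -(8/12)e = -(2/3)e, or -(2/9)e on the three-video mean. For e = 0.05, 0.10 and 0.20 SD that is -0.011, -0.022 and -0.044. The clip's own effect on that mean with d2 = -0.10 and d3 = -0.05 is -0.05. A positive e makes the clip look worse; a negative e makes it look better. The clip causes neither.

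**The case against.** The strongest objection is that the stated hypotheses on the CDC clip do not rest on this index, and that much of it stands. A reader might infer that hypotheses 4 and 5 in Section 3 are undermined. The documents do not support that. Hypothesis 4 concentrates on outcomes tied to the distancing and hygiene video: if these are the (SD-H) outcomes, they lie outside family 1, and if they are Video 2's own ratings, Video 1 is already out. Hypothesis 5 compares attitudes to masks.

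A reader might also infer that the mask-debiasing result is diluted. Main test 5 uses mask outcomes, so no dilution is shown there; the earlier ratings offer extra precision only.

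Three further points have weight.

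- No sentence says that the index averages three videos. Pooling is inferred from an unsplit family with a planned index, and since viewing time is also in the family, a one-third share for Video 1 is an assumption. A common response scale across videos is likewise inferred.
- A Videos 2-3 index is itself diluted if only Video 2 responds, as the d3 = 0 column shows.
- An all-video average is a valid estimate of the effect on the whole package, which suits the search for the best combination. Dilution is not bias in that use.

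The last point does not rescue tests 3 and 4, which ask what the clip does. Nor does the Lasso check: it does not expressly exclude earlier ratings, but it is only a robustness step.

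**Conclusion.** The concern holds for family 1 in main tests 3 and 4 and in the CDC-clip interactions, provided that the index pools all three videos. In cells 2/6 v 1/5 the Video 1 part has a true clip effect of zero by design and weakens the result. It would be wrong to carry that zero over to test 4, where Video 1 differs between the sides because of elephant content; the error there can go either way and can offset or exceed the dilution.

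The timing is certain from the documents. The size is illustrative: it rests on assumed correlation, effects, weights, alpha and control share. The sample penalty against an adjusted Videos 2-3 index is about 1.9 times at rho 0.2, 3.0 at 0.5 and 5.0 at 0.7. The point is worth correcting because a better analysis is available from data the survey already collects. It does not threaten the trial's other outcome families.

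**What to change.** In Sections 5.2 and 5.3:

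- State which videos enter family 1 for each contrast.
- For CDC-clip contrasts on family 1, make Video 2 ratings and viewing time the main measure, report Video 3 separately for carry-over, and leave Video 1 out of the outcome.
- Estimate the clip effect in cells 2/6 v 1/5, or with elephant indicators in the model, and adjust for Video 1 rating and viewing time. Dropping Video 1 alone would not clear test 4 of any elephant carry-over into later ratings.
- Report Video 1 as a placebo outcome in the same cells. A difference among analysed respondents would point to selection, through drop-out or the quality exclusions in Section 4.2.
- For mask-debiasing contrasts, add Video 1 and 2 ratings as precision covariates only; the gain is not quantified here.
- Do not adjust for these ratings in the concordance, elephant or treatment-v-control contrasts, where they are post-treatment.

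No new data are needed. The cost is that family 1 has a different composition by contrast, so its effects are not directly comparable across factors. An all-video index can be kept for choosing the best combination.
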